4.15 Standard of Truth

The SoT algorithm is explained in Section 3.2.

The SoT of PET positive lesions identified by local investigator will be listed by subject, region and lesion showing each of the four steps, as applicable, including final assessment (positive/negative/unknown). Lesions for which only part of the SoT steps are performed will be listed including the step(s) which is/are not performed. Lesions for which no SoT is performed will be listed including Step 1 and 2.

The central read of SoT will be listed by subject and will include SoT proven, with reason(s) for justification. In addition, a listing will be provided showing the modality of the reason, combining

Parexel International

Blue Earth Diagnostics Ltd
BED-PSMA-302

Statistical Analysis Plan

local histology and central read consensus reasons. Finally, a listing will be made of lesion size, including detection by blinded PET reader. The central SoT read will be summarized by region.

The SoT of PET positive lesions identified by the blinded independent PET readers will be listed by subject, reader, region and lesion, showing result for either of three steps: Histological SoT (Step 1) or historical and baseline Imaging SoT (Step 2) or confirmatory Imaging SoT (Step 3 and 4). Any PET positive lesion deemed not a TP according to the SoT will be declared a FP.

The SoT at a region level will be listed by subject, blinded PET reader and region, including SoT result. Regions where no lesion(s) were identified will not be listed. PET positive regions where no SoT positive lesions are present will be FP. PET positive regions with one or more SoT positive lesion(s) will be TP. PET negative regions with one or more SoT positive regions will be FN.

The SoT at a region level will be summarized by blinded PET reader and region using the EAP. The summary will include the number of subjects with positive lesions per region, the number of TP, FP patients per region, the PPV for the regions, including 95% two-sided CIs using the clustered binary data algorithm (Section 4.16.1.3).

Patient level SoT will be listed by subject, blinded PET reader, including result. Patients where no positive lesion(s) were identified by both PET and SoT will not be listed.

Patient level SoT will be summarized by blinded PET reader using the EAP. The summary will include the CDR, including two-sided exact 95% CIs.

An additional summary will show at which step the SoT was determined by the local investigator.

Central read of SoT involving the blinded independent PET readers who did not complete the full set of rhPSMA-7.3 (¹⁸F) PET reads will only be listed.

The imaging SoT will be matched with the blinded PET reader based on the lesion ID for each reader as identified by the SoT panel, and the histopathology finding by the investigator (as recorded on CRF) will be matched with the blinded PET reader finding based on the anatomical location of the lesion. Histopathology finding will only be used if within a 60 days window relative to the PET scan. Location and region of lesions as determined by the blinded PET reader will be used in all listings and tables.

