4.16 Efficacy Evaluation

4.16.1 Analysis and Data Conventions

This study success criteria are based upon the diagnostic performance of rhPSMA-7.3 (¹⁸F) PET exceeding pre-specified minimum thresholds for the co-primary endpoints of patient level CDR and region level PPV. The joint hypothesis, based on the assumptions as outlined in Section 4.18.1, is as follows:

$$H_0: \text{CDR} \leq 36.5\% \text{ or } \text{PPV} \leq 62.5\% \text{ versus } H_1: \text{CDR} > 36.5\% \text{ and } \text{PPV} > 62.5\%$$

For CDR, exact intervals and exact binomial tests will be used in the analysis.

As PPV is a by-region endpoint, patients may have one to three regions that may be included in the PPV assessment. Thus, variance estimated will be adjusted based on clustering of regions within a patient ([Zhou, Obuchowski, and McClish, \(2002\), pg 104](#)). An asymptotic normal distribution will be used to test the PPV hypotheses.

Parexel International

Blue Earth Diagnostics Ltd
BED-PSMA-302

Statistical Analysis Plan

For the study to be considered a success, the p-values for both endpoints must be statistically significant ($P < 0.025$) for at least two out of the three blinded image evaluation readers (same readers for both CDR and PPV).

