4.16.3 Secondary Efficacy Variables

4.16.3.1 Patient level CDR and region level PPV of rhPSMA-7.3 (^{18}F) PET in the subgroup of patients who have negative baseline conventional imaging.

This will be a repeat of the primary efficacy using patients from the EAP with negative baseline conventional imaging (according to site reads). The point estimates and two-sided 95% CIs of CDR and PPV will be displayed for each of the blinded independent readers and their majority.

4.16.3.2 Patient level CDR and region level PPV of rhPSMA-7.3 (^{18}F) PET for recurrence in those patients with and without reference standard histopathology available.

For CDR, this will be repeats of the primary efficacy using patients from the EAP and one more condition:

1. Patients with standard histopathology for SoT assessment
2. Patients with no standard histopathology for SoT assessment

For PPV, this will be repeats of the primary efficacy using patients from the EAP and one more condition:

1. Regions with standard histopathology assessment
2. Regions with no standard histopathology assessment

The point estimates and two-sided 95% CIs of CDR and PPV will be displayed for each set of patients for each of the blinded independent readers and their majority.

4.16.3.3 Patient level CDR and region level PPV of rhPSMA-7.3 (^{18}F) PET stratified by PSA level.

This will be repeats of the primary efficacy using patients from the EAP. The last PSA level before the PET scan will be used to stratify the patients (see Section 4.10 for categories). The point estimates

Parexel International

Blue Earth Diagnostics Ltd

BED-PSMA-302

Statistical Analysis Plan

and two-sided 95% CI of CDR and PPV will be displayed for each set of patients for each of the blinded independent readers and their majority.

4.16.3.4 CDR of rhPSMA-7.3 (¹⁸F) PET in the following regions: local recurrence, pelvic lymph nodes, other.

This analysis will use the EAP. The analysis will be performed for each region and for each of the blinded independent readers and their majority. The frequency of confirmed detection will be summarized, including proportion and exact CI of the proportion.

4.16.3.5 Percentage of patients in whom rhPSMA-7.3 (¹⁸F) PET imaging results changed the intended patient management (major and other changes).

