4.16.4 Exploratory Efficacy Variables

4.16.4.1 The overall patient level detection rate (without SoT confirmation), including detection rate subgroup analyses of patients: a) who have negative baseline conventional imaging (according to site read), b) with reference standard histopathology available and unavailable, and detection rate stratified by PSA level and assessed by region.

This concerns several similar analyses. In each analysis the frequency of patients with a PET positive lesion will be counted, proportion of positive patients including exact CI will be provided. Each analysis will be performed for each of the blinded independent readers and their majority.

- patients in the FSP who have PET scan and who have negative (no lesions detected at all) baseline conventional imaging.
- patients in the FSP who have PET scan and have reference standard histopathology.
- patients in the FSP who have PET scan and do not have reference standard histopathology.
- For each region (local recurrence, pelvic lymph nodes, other) patients in the FSP who have PET scan using subgroups by PSA levels (Section 4.10).

4.16.4.2 Patient level PPV in which a TP patient is defined as having at least one TP region, regardless of any coexisting FP regions.

This concerns all patients in the EAP. The patient level PPV frequency and proportion, including exact CIs will be provided for each of the blinded readers and their majority.

4.16.4.3 The number of positive rhPSMA-7.3 (¹⁸F) scans compared to conventional imaging in defined regions, leading to upstaging of the patient a) post-RP; b) post--RT.

This concerns patients with negative baseline scan in subgroups of the EAP with an extra subgroup condition, for a) the patient has had RP (with or without RT), for b) the patient has had RT (without RP) or c) patient has other therapies. (For definitions of RT and RP, see Section 4.8). The patients will be counted if they have any TP lesion in either of the regions (local recurrence, pelvic lymph nodes, other) for each of the blinded readers and their majority.

4.16.4.4 Patient and regional level detection rates of rhPSMA-7.3 (¹⁸F) PET.

This concerns the subgroup of patients in the FSP who have a PET scan. The regions analysis will concern local recurrence, pelvic lymph nodes and other. The frequency of detection, detection rate including exact CI will be determined for each of the blinded readers and their majority.

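### The by-region PPV table in SAP 4.15 uses the clustered normal CI where no clustering exists, so each single-region interval is a plain Wald interval with somewhat low coverage; an exact interval fits directly

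*SAP*

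**What the plan says.** SAP 4.15 sets the level of the table: "The SoT at a region level will be summarized by blinded PET reader and region using the EAP". The table is to show counts of TP and FP patients in each region and "the PPV for the regions, including 95% two-sided CIs using the clustered binary data algorithm (Section 4.16.1.3"). The same section reduces each PET-positive region to a single result: "PET positive regions with one or more SoT positive lesion(s) will be TP", and otherwise it is FP.

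SAP 4.16.1 explains why a clustered variance is used for PPV: "patients may have one to three regions that may be included in the PPV assessment", and hence the "variance estimated will be adjusted based on clustering of regions within a patient". SAP 4.16.1.3 gives the variance estimator and a symmetric interval with normal quantiles. Its subsection 4.16.1.3.1 acknowledges that the bounds may fall outside 0 to 1 and adds an interval on the logit scale.

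For closely related proportions the SAP specifies exact intervals. For CDR by region (4.16.3.4): "The frequency of confirmed detection will be summarized, including proportion and exact CI of the proportion". For PPV by patient (4.16.4.2): "The patient level PPV frequency and proportion, including exact CIs will be provided for each of the blinded readers and their majority". The patient-level CDR in 4.15 is also given an exact interval.

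**The concern.** The clustering adjustment answers a problem that arises only when the three regions are pooled, because one patient may then supply up to three correlated results. Within a single region a patient supplies one result or none. The results are independent binary outcomes, and nothing remains to adjust. What the algorithm leaves behind is its normal approximation, which is weakest where counts are small or the proportion is high.

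At stake is the table that tells readers how far a positive finding in the prostate bed, the pelvic nodes or elsewhere can be trusted. Its intervals would carry a 95% label that they do not always earn, and the errors run mainly in the flattering direction, with lower limits set too high. The TP count in a region would also get a normal interval when it is the numerator of PPV and an exact one when it is the numerator of CDR, with no reason given.

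**Working it through.** **The plan's own figures.** The documents state nothing about the by-region intervals. The nearest stated figure is the power for the pooled PPV (SAP 4.18.2): 190 positive cases, 73.5% against 62.5%, exact one-sided test at 0.025. The critical count is 133, the actual alpha 0.0185 and the power 87.9%, against a stated value above 88%. The 0.1-point difference has no bearing here.

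**Step 1: the variance with one result per patient.** SAP 4.16.1.3 gives

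Var = [1/(P(P-1))] × Σ (Pos_p / mean Pos)² × (PPV_p − PPV)².

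In a single region, over the PET-positive patients, Pos_p = 1 for all, the mean is 1, and PPV_p is 0 or 1. Write p for the observed PPV. The sum is then P·p(1−p), so

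Var = p(1−p)/(P−1).

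For 36 TP out of 40, 0.9 × 0.1/39 = 0.0023077, and the SAP formula gives the same value. The interval p ± 1.96·√Var is a Wald interval with P−1 in place of P.

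**Step 2: coverage.** Counts per region are not in the documents, so n is an assumption. Planning PPVs are 65% (PSA <1 ng/mL), 73.5% (overall) and 80% (PSA ≥1 ng/mL), from SAP 4.18.1; 90% is added as a stress case. Coverage is the sum of binomial probabilities over all counts whose interval contains the true PPV.

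| n | PPV 65% | 73.5% | 80% | 90% |
|---|---|---|---|---|
| 20 | 93.6% | 90.9% | 92.1% | 87.6% |
| 30 | 91.1% | 91.6% | 94.6% | 80.9% |
| 40 | 95.3% | 91.4% | 90.5% | 91.5% |
| 60 | 94.1% | 93.2% | 92.2% | 94.1% |
| 80 | 93.9% | 93.9% | 93.2% | 90.0% |
| 100 | 94.0% | 94.6% | 93.3% | 93.2% |

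The 87.6% at n = 20 and PPV 90% says little about ordinary counts. The outcome 20/20 has probability 0.9^20 = 12.2% and gives a zero-width interval, which accounts for nearly all of the 12.4% missed. At n = 30 and PPV 90%, the all-TP outcome accounts for 4.2 of the 19.1 points missed.

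**Step 3: direction of the misses.** At a true PPV of 73.5%, the lower limit lies above the truth with probability 7.0% (n = 20), 7.0% (n = 30), 6.5% (n = 40) and 5.2% (n = 60), against a nominal 2.5%.

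**Step 4: the alternatives.** Over n = 15 to 150 and PPV 60% to 95%, Clopper-Pearson covers 95.4% to 99.5%. The SAP's logit interval, coded as in Appendix 6.1, covers 94.7% to 97.7% for n = 20 to 100 at PPV 65% to 80%. It drops to 83.5% at n = 20 and PPV 90% (counting undefined intervals as misses), and does not exist at 0/n or n/n.

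| TP/n | Normal CI (4.16.1.3) | Logit CI (4.16.1.3.1) | Exact CI |
|---|---|---|---|
| 18/20 | 76.5% to 103.5% | 66.8% to 97.6% | 68.3% to 98.8% |
| 27/30 | 79.1% to 100.9% | 72.8% to 96.8% | 73.5% to 97.9% |
| 29/40 | 58.5% to 86.5% | 56.6% to 84.2% | 56.1% to 85.4% |
| 44/60 | 62.0% to 84.6% | 60.7% to 83.0% | 60.3% to 83.9% |

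At a true PPV of 73.5%, the normal upper bound passes 100% with probability 18% at n = 20, 2.5% at n = 30, 0.3% at n = 40 and practically zero from n = 60.

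**The case against.** The SAP has already seen the range problem. The section that 4.15 cites contains 4.16.1.3.1, which supplies a bounded interval with good coverage at the planning PPVs. This largely stands: a reader might infer from 103.5% that the SAP would knowingly publish impossible bounds with no remedy, and the documents do not support that. What remains is that 4.15 does not say whether the logit interval is shown in this table, that the normal interval stays in any case, and that the logit interval fails when all results are TP or all are FP.

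The sizes depend on assumed counts. The plan expects 190 positive patients with more than one positive region on average, so three regions average at least 190/3, or about 63 positives each. At that size and PPV 65% to 80% the shortfall is about 0.4 to 3 points. This stands as well, although an average of 63 does not stop one region from being much smaller.

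Single-region PPV is not a listed endpoint and has no test. That stands, and it limits the weight of the point. A reader might go further and infer that the co-primary PPV or the success rule is compromised. It is not: the pooled PPV has real clustering and the adjustment belongs there.

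The phrase on PPV for the regions could be read as the pooled PPV. The preceding sentence and the counts beside it point to a by-region table. If the pooled PPV was meant, 4.15 should say so.

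Finally, one algorithm for all PPV tables is a tidy convention and remains valid in large samples, while exact intervals are conservative (about 99% at n = 20 to 30 and PPV 90%). That is a fair cost to name, but the SAP already accepts it for region-level CDR and patient-level PPV.

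**Conclusion.** The point holds as a minor one. As written, 4.15 gives PPV within one body region an adjustment with nothing to adjust, and the result is a Wald interval. If a region has 20 to 40 positives, true coverage is about 91% to 92% at a PPV of 73.5%. With 60 to 100 positives and a PPV of 65% to 80% it is about 92% to 95%. Larger shortfalls need a small region or a PPV near 90% or above. These figures rest on assumed counts per region and on independence between patients. The algebra in step 1 needs neither. No test, endpoint or success criterion changes.

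**What to change.** In SAP 4.15, state that PPV within each single body region, for each reader and for the majority read, is reported with a two-sided exact (Clopper-Pearson) 95% CI, as in 4.16.3.4 and 4.16.4.2. Keep the clustered interval of 4.16.1.3 and the logit interval of 4.16.1.3.1 for PPV pooled over regions, and say in which tables the logit interval appears.

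The cost is one sentence and a standard software option. The single-region intervals become somewhat conservative and usually slightly wider: 44/60 goes from a width of 22.6 points (62.0% to 84.6%) to 23.6 points (60.3% to 83.9%).

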4.16 Efficacy Evaluation

4.16.1 Analysis and Data Conventions

This study success criteria are based upon the diagnostic performance of rhPSMA-7.3 (¹⁸F) PET exceeding pre-specified minimum thresholds for the co-primary endpoints of patient level CDR and region level PPV. The joint hypothesis, based on the assumptions as outlined in Section 4.18.1, is as follows:

$$H_0: \text{CDR} \leq 36.5\% \text{ or } \text{PPV} \leq 62.5\% \text{ versus } H_1: \text{CDR} > 36.5\% \text{ and } \text{PPV} > 62.5\%$$

For CDR, exact intervals and exact binomial tests will be used in the analysis.

As PPV is a by-region endpoint, patients may have one to three regions that may be included in the PPV assessment. Thus, variance estimated will be adjusted based on clustering of regions within a patient ([Zhou, Obuchowski, and McClish, \(2002\), pg 104](#)). An asymptotic normal distribution will be used to test the PPV hypotheses.

Parexel International

Blue Earth Diagnostics Ltd
BED-PSMA-302

Statistical Analysis Plan

For the study to be considered a success, the p-values for both endpoints must be statistically significant ($P < 0.025$) for at least two out of the three blinded image evaluation readers (same readers for both CDR and PPV).

4.16.1.1 Parameters of efficacy

Considering the definition table (Table 6), based on the categorization of lesions, the patients and regions can be categorized.

Table 6: Definitions of true and false positive and true and false negative lesions

		True assessment		
		Positive	Negative	Total
PET scan assessment	Positive	TP	FP	TP+FP
	Negative	FN	TN	FN+TN
	Total	TP+FN	FP+TN	$\begin{matrix} N \\ (=FP+TP+TN+FN) \end{matrix}$

FN=False Negative, TN=true Negative

The data does not provide separate counts of TN and FN, however, the sum of TN and FN is known, as this is the number of PET negative scans or patients. N is therefore the total number of patients with PET scan assessment.

CDR is defined as the percentage of all patients scanned who have at least one TP lesion. Hence $CDR = TP/N$.

PPV is defined as the regions which are true positive out of all regions with positive region. Hence $PPV = TP/(TP+FP)$.

Detection rate is the proportion of PET scan positive relative to total (number of patients or number of regions, depending on endpoint). Hence this is $(TP+FP)$ out of the total population (which would be N for the EAP).

4.16.1.2 Handling of missing data

4.16.1.2.1 Primary analysis

Patients who have no positive lesions identified by the blinded independent PET readers do not have missing data. They will not be counted for PPV as they are neither TP nor FP. They will count in the denominator of CDR, since they are either FN or TN.

Positive lesions which do not get confirmed via the SoT will be designated as FP by the SoT algorithm. By extension, positive lesions which are missing both histopathology and sufficient scans to determine the SoT will be declared FP.

Parexel International

Blue Earth Diagnostics Ltd
BED-PSMA-302
4.16.1.2.2 Other

Statistical Analysis Plan

Section 4.8 contains information on date imputation to decide if medications and procedures are prior or concomitant.

Section 4.17.1 contains information on date imputation to decide if an AE is treatment emergent. It also describes imputation for missing toxicity grading or causality.

Section 4.10 contains information on date imputation for calculation of PSAdt.

4.16.1.3 Clustered binary data estimate of variance

Following Zhou et al. the following estimators will be used:

$$\widehat{PPV} = \sum_p TP_p / \sum_p Pos_p$$

$$\widehat{Var}(\widehat{PPV}) = \frac{1}{P(P-1)} \sum_p \left(Pos_p / \overline{Pos} \right)^2 (\widehat{PPV}_p - \widehat{PPV})^2$$

With:

P	: (number of) Patients
p	: individual patient
Pos_p	: Number of positive regions for patient p
TP_p	: Number of true positive regions for patient p
$\overline{Pos} = \sum_p Pos_p / P$: Mean cluster size
$\widehat{PPV}_p = TP_p / Pos_p$: Patient PPV

The example in Zhou et al. is coded in SAS in Appendix 6.1.

An asymptotic normal distribution for the sampling distribution of \widehat{PPV} is assumed and the 95% confidence interval will be derived as:

$$\widehat{PPV} \pm Z_{1-\alpha/2} \sqrt{\widehat{Var}(\widehat{PPV})}$$

where $Z_{1-\alpha/2}$ is the upper $1-\alpha/2$ value for the standard normal distribution.

Furthermore, p-value for the primary hypothesis test will be obtained by

$$p\text{-value} = 1 - \Phi \left(\frac{\widehat{PPV} - 0.625}{\sqrt{\widehat{Var}(\widehat{PPV})}} \right)$$

Where $\Phi()$ is the CDF of the standard normal distribution calculated at the critical point.

4.16.1.3.1 Additional Confidence interval

Normal approximation in constructing 95% CIs might lead to bounds exceed [0, 1] for \widehat{PPV} . Hence an additional CI will be derived. Logit transformation will be applied to PPV and Delta Method (Casella and Berger, 2021) will be utilized to obtain to approximate the variance of $\text{logit}(PPV)$. Accordingly, the asymptotical distribution of $\text{logit}(PPV)$ is

$$\sqrt{n} \left[\log \left(\frac{\widehat{PPV}}{1-\widehat{PPV}} \right) - \log \left(\frac{PPV}{1-PPV} \right) \right] \xrightarrow{d} N \left(0, \frac{1}{[PPV(1-PPV)]^2} Var(PPV) \right).$$

Parexel International

Blue Earth Diagnostics Ltd
BED-PSMA-302

Statistical Analysis Plan

Accordingly, an asymptotic normal distribution for the sampling distribution of $\text{logit}(\bar{PPV})$ is assumed and the 95% confidence interval will be derived as:

$$\text{logit}(\bar{PPV}) \pm Z_{1-\alpha/2} \sqrt{\widehat{\text{Var}}(\text{logit}(\bar{PPV}))}$$

where $Z_{1-\alpha/2}$ is the upper $1-\alpha/2$ value for the standard normal distribution and $\sqrt{\widehat{\text{Var}}(\text{logit}(\bar{PPV}))} \approx \frac{1}{[\bar{PPV}(1-\bar{PPV})]^2} \widehat{\text{Var}}(\bar{PPV})$. Lower and upper confidence intervals values will be reported in [0,1] scale by the logit inverse transformation, as follows

$$CI_{[0,1] \text{ scale}} = \frac{e^{CI_logit}}{1 + e^{CI_logit}}$$

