4.19 Changes in the Conduct of the Study or Planned Analysis

The EPSP has been added in the analysis populations for analyzing the PET scan imaging irrespective of standard of truth.

4.19.1 Changes in the Conduct of the Study or Planned Analysis Due to COVID-19

This study was conducted during the COVID-19 global pandemic (the official date of the pandemic being over has not been identified at the time of writing this SAP), which may have influenced study conduct at the investigational sites.

Missed visits and any data collection interference will be captured on a specific page of the CRF and protocol deviations due to COVID-19 will be listed separately. Any impact on the populations, endpoints and analyses will be assessed and reported on in the CSR under a specific section.

5 References

- [2] Casella, G, Berger R L Statistical inference. Cengage Learning, 2021
- [3] Guidance for Industry and FDA Staff - Statistical Guidance on Reporting Results from Studies Evaluating Diagnostic Tests (13 March 2007) Retrieved 15 March 2019, <https://www.fda.gov/media/71147/download>
- [5] SAS® Version 9.3 of the SAS System for Personal Computers. Copyright ©2011-. SAS Institute Inc. SAS and all other SAS Institute Inc. product or service names are registered trademarks or trademarks of SAS Institute Inc., Cary, NC, USA.
- [7] Zhou XH, Obuchowski NA and McClish, DK. Statistical Methods in Diagnostic Medicine. Wiley, New York, 2002 pp 104-6

Parexel International

Blue Earth Diagnostics Ltd
BED-PSMA-302
6 Appendix

Statistical Analysis Plan

6.1 SAS program to reproduce data in Zhou et al [6].

```

data one;
input TN      No_Polyps;
Cards;
1      1
2      2
2      2
1      1
2      2
2      2
1      1
1      1
1      1
1      1
2      2
0      1
2      3
2      2
1      1
1      1
1      1
2      2
0      2
1      1
2      2
2      2
2      2
0      1
;;;;;
run;

proc sql;
  create table two as
  select
    TN ,
    No_Polyps,
    TN/No_Polyps as Sei_hat,
    Se_hat,
    No_Polyps/mNo as Ni_N,

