    (calculated Ni_N)*(calculated Ni_N)
      * (calculated Sei_hat-Se_hat)* (calculated Sei_hat-Se_hat) as fc,
    sum(calculated fc) as sfc,
    calculated sfc/(n*(n-1)) as varSe_hat
  from
    (select
      sum(TN) as sTN,
      sum(No_Polyps) as sNo,
      mean(No_Polyps) as mNo,
      count(*) as n,
      calculated sTN/calculated SNo as Se_hat
      from one ) as o,
    one;
  quit;

data final;
  set two;
  if n_=1;
  CI_L = Se_hat - (quantile('NORMAL', .975)*varSe_hat**0.5);
  CI_U = Se_hat + (quantile('NORMAL', .975)*varSe_hat**0.5);
  p_value = 1 - CDF('NORMAL', (Se_hat-0.625)/varSe_hat**0.5);
  keep Se_hat varSe_hat CI_L CI_U p_value;
run;

```

Parexel International

Blue Earth Diagnostics Ltd

BED-PSMA-302

data final_logit;

```
  set final;
  logit_Se_hat = log(Se_hat/(1-Se_hat));
  logit_varSe_hat = varSe_hat*((1/(Se_hat*(1-Se_hat)))**2);
  logit_CI_L = logit_Se_hat - (quantile('NORMAL', .975)*logit_varSe_hat**0.5);
  logit_CI_U = logit_Se_hat + (quantile('NORMAL', .975)*logit_varSe_hat**0.5);
  logit_zero_one_CI_L = (CONSTANT('E')**logit_CI_L)/((CONSTANT('E')**logit_CI_L)+1);
  logit_zero_one_CI_U = (CONSTANT('E')**logit_CI_U)/((CONSTANT('E')**logit_CI_U)+1);
run;
```

Statistical Analysis Plan

Parexel International

Blue Earth Diagnostics Ltd
BED-PSMA-302

Statistical Analysis Plan

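### SAP 4.16.1.3.1 sets the standard error of logit(PPV) equal to its variance (a square root is missing), against the SAP's own code; only the additional PPV interval is affected

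*SAP*

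**What the plan says.** SAP section 4.16.1.3 gives the clustered variance of PPV, a normal-approximation 95% interval on the raw scale and the primary p-value against 0.625. Section 4.16.1.3.1 notes that raw-scale limits can fall outside 0 to 1 and continues: "Hence an additional CI will be derived".

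That section then makes four statements:

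- The delta method "will be utilized to obtain to approximate the variance of $\text{logit}(PPV"), so its stated target is a variance.
- The limiting distribution is written with the expression in the variance position: "N \left(0, \frac{1}{[PPV(1-PPV)]^2} Var(PPV").
- The interval is "logit}(\bar{PPV}) \pm Z_{1-\alpha/2} \sqrt{\widehat{\text{Var}}(\text{logit}(\bar{PPV"))), that is, the estimate plus or minus z times a standard error.
- The standard error is then defined by a clause whose left side stands under a square root and whose right side does not: "Var}}(\text{logit}(\bar{PPV}))} \approx \frac{1}{[\bar{PPV}(1-\bar{PPV})]^2} \widehat{\text{Var}}(\bar{PPV").

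Appendix 6.1 contains SAS code for the same interval. It computes "logit_varSe_hat = varSe_hat*((1/(Se_hat*(1-Se_hat)))2") (the final 2 is an exponent), then the lower limit as "logit_CI_L = logit_Se_hat - (quantile('NORMAL', .975)*logit_varSe_hat0.5") (the final 0.5 is an exponent). The upper limit is built the same way.

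**The concern.** The last clause of section 4.16.1.3.1 uses a variance where a standard error is needed. It disagrees with the limiting distribution printed a few lines above it and with the appendix code.

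The clause is the only explicit formula in the text for the quantity multiplied by z. The text does not point to the appendix for this interval, and the appendix is headed as a "SAS program to reproduce data in" the cited textbook, not as production code for the trial. SAP section 4.1 requires independent checking of outputs. A programmer or checker who works from the written formula would either fail to match the code or report an interval labelled 95% that is far too narrow. The interval belongs to a co-primary endpoint that is analysed for each of three readers and for their majority, so the error could repeat across outputs.

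**Working it through.** **Delta method.** With g(p) = log[p/(1 − p)], g′(p) = 1/[p(1 − p)]. Hence

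- Var(logit PPV) = Var(PPV) / [PPV(1 − PPV)]²
- SE(logit PPV) = sqrt(Var(PPV)) / [PPV(1 − PPV)]

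The printed clause assigns the first expression to the second quantity. The documents report no numerical value for this interval, so there is no stated figure to reproduce. Both versions are run below.

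**1. The SAP's own example (Appendix 6.1 data).** There are 24 patients and 37 units, of which 32 are correct.

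- Estimate: 32/37 = 0.8649; logit = 1.8563
- Clustered variance by the section 4.16.1.3 formula: 0.004386
- Var(logit) = 0.004386 / (0.8649 × 0.1351)² = 0.3211
- SE(logit) = sqrt(0.3211) = 0.5667
- As coded: 1.8563 ± 1.96 × 0.5667, back-transformed: **67.8% to 95.1%**
- As printed: 1.8563 ± 1.96 × 0.3211, back-transformed: **77.3% to 92.3%**

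**2. Planning values (SAP 4.18.2).** PPV is 73.5% with 190 positive cases. I assume one positive region per patient, in which case the clustered variance reduces to p(1 − p)/(n − 1).

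- Var(PPV) = 0.735 × 0.265 / 189 = 0.001031
- Var(logit) = 1 / (189 × 0.735 × 0.265) = 0.0272; SE(logit) = 0.1648
- logit(0.735) = 1.0201
- Correct: 1.0201 ± 1.96 × 0.1648, giving **66.8% to 79.3%**
- As printed: 1.0201 ± 1.96 × 0.0272, giving **72.5% to 74.5%**, 6.05 times narrower
- Coverage by exact binomial enumeration at a true PPV of 73.5%: **95.2%** correct, **25.7%** as printed

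**3. Dependence on size.** The printed half-width on the logit scale is the correct one multiplied by SE(logit), so the error grows as the sample grows. At 73.5%, again with one region per patient:

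| Regions | Correct | As printed | Coverage, correct / printed |
|---|---|---|---|
| 190 | 66.8–79.3% | 72.5–74.5% | 95% / 26% |
| 50 | 59.5–84.0% | 69.3–77.3% | 96% / 47% |
| 20 | 50.0–88.5% | 62.0–82.5% | 98% / 81% |

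The two versions coincide when Var(logit) = 1, that is n = 1 + 1/(0.735 × 0.265) = 6.1. Below about six regions the printed interval is the wider one.

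**4. Clustering.** The documents give neither the number of positive regions per patient nor the within-patient correlation. I therefore assumed 190 positive patients with 1 to 3 regions each (mean 1.0 to 1.7) and an intraclass correlation from 0 to 0.95. A beta-binomial simulation with 20,000 runs per setting gave coverage of 19% to 28% for the printed formula and 94% to 95% for the code.

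**5. Scope.** The raw-scale interval and the p-value in section 4.16.1.3 use sqrt(Var(PPV)) directly. The success rule in sections 4.16.1 and 4.16.2 rests on p-values. None of them uses the logit standard error.

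**The case against.** The algebra and the arithmetic are not in dispute. The case on the other side has three parts.

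- **The radical may be a reading artefact.** The text was extracted from PDF by a program, and the notation here is unstable: the estimator carries a hat at first and a bar after the page break. A stray radical cannot be excluded. This stands as a caveat, and the source file should be checked first. Nothing shows that the radical is an artefact, however, and in the text as supplied both the radical and the squared denominator are explicit.
- **The rest of the section and the code are right.** The stated aim, the limiting distribution, the interval line and Appendix 6.1 all agree. The revision history records that formulas and SAS code were added together, and the code tests against 0.625, this trial's null value. It is fair to say that one clause is at odds with everything around it and that the intended method is clear. That makes the correction easy. It does not make the clause correct, and the clause is where the text tells the reader what to compute.
- **Harm is unlikely.** If the appendix code is run, the reported interval is correct. If the clause were followed, an additional interval of 72.5% to 74.5% beside a raw-scale interval of about 67.2% to 79.8% would be noticed. That is a good reason to rate the point low, and it is rated low.

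**Conclusion.** The concern holds as a minor error. As written, the SAP defines the standard error of logit(PPV) by its variance and contradicts its own code. Taken literally at the planned size, the additional interval would be about one sixth of its proper width and would cover the true PPV about 26% of the time instead of 95%. That figure assumes a true PPV of 73.5%, 190 positive cases and one region per patient; across the assumed clustering settings the coverage is 19% to 28%. The primary PPV interval, the p-value, the success decision, power and sample size are unaffected. The conclusion depends on the radical being present in the source PDF. If it is absent there, the clause correctly defines the variance and the point falls away.

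**What to change.** Check the clause in the source file. If the radical is there, replace the clause in SAP section 4.16.1.3.1 with SE(logit PPV) = sqrt(Var(PPV)) / [PPV(1 − PPV)], or remove the root on the left so that the clause defines the variance. Either makes the text agree with Appendix 6.1. A sentence in section 4.16.1.3.1 pointing to that code would remove any doubt about which governs. The cost is one formula in the SAP text, with no change to code, primary test, power, sample size or timeline.
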